Figure 14.6 Association of Change in Nonvellus Target Area Average Hair Width with Subject Self Assessment, ITT Population

For the following plot change nonvellus target area hair count (vertical), change nonvellus target area hair width (vertical) and change nonvellus target area average hair width (vertical), vs time since diagnosis of androgenetic alopecia [4 figures on page – all timepoints on page] Indicate timepoint at top of each of the visits. Separate color for males and females and linear regression line as per figure 14.1.Add Foonote: Note Lines represent fit linear regression line.

Figure 14.7	Association of Change in Nonvellus Target Area Hair Count with Time Since Diagnosis of Androgenetic Alopecia, ITT Population
Figure 14.8	Association of Change in Nonvellus Target Area Hair Width with Time Since Diagnosis of Androgenetic Alopecia, ITT Population
Figure 14.9	Association of Change in Nonvellus Target AreaAverage Hair Width with Time Since Diagnosis of Androgenetic Alopecia, ITT
Population	

23 Apr 2019 Statistical Analysis Plan

Protocol: ATI-50002-AGA-201

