**1. SYNOPSIS**

Name of Sponsor/Company: Aclaris Therapeutics, Inc.

Name of Investigational Product: ATI-50002 Topical Solution 0.46%

Title of Study: An Open-Label Safety, Tolerability, and Efficacy Study in Male and Female Subjects with Androgenetic Alopecia Treated with ATI-50002 Topical Solution

Study center(s): Approximately 3 investigational centers will participate in the study.

Phase of development: Phase 2a

Objectives:
 
Primary:
 
 
• To assess safety, tolerability and efficacy of ATI-50002 Topical Solution, 0.46% in male and female subjects with androgenetic alopecia (AGA)
 
 
Secondary:
 
 
• To assess the development of new hair growth/scalp coverage as assessed by the investigator and the subject using a seven-point rating scale and global scalp photographs.
 
• To assess the change from baseline in cumulative target area hair width
 
• To assess the change from baseline in androgenetic alopecia stage according to the Norwood-Hamilton scale in males and the Sinclair Scale in females.
 

Study Design:
 
This is an open-label phase 2 study designed to evaluate the safety and efficacy of ATI-50002 Topical Solution, 0.46% in male and female subjects with androgenetic alopecia. Subjects will be required to apply ATI-50002 study medication to their scalp twice a day for a total of 26 weeks. Upon completion of the first 26 weeks of treatment, subjects will have the option to consent to continue on study medication for an additional 26 weeks of treatment. All subjects will be required to complete a safety follow up visit 4 weeks after last application of study medication.
 
A total of 24 subjects (approximately 12 males and 12 females) ages 18-50 years with a clinical diagnosis of AGA will be enrolled in the study. Male subjects must have a Norwood classification of Type III vertex, IV or V and woman must have a Sinclair Grade of 2, 3 or 4.

Number of patients (planned): Approximately 12 male subjects and 12 female subjects will be enrolled to the study.

Inclusion Criteria: Subjects must meet the following criteria to be eligible for participation in the study:
 
 
1. Able to comprehend and willing to sign an Informed Consent Form (ICF).
 

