## **7. INVESTIGATIONAL PLAN**

### **7.1. Overall Study Design**

This is an open-label phase 2 study designed to evaluate the safety and efficacy of ATI-50002 Topical Solution, 0.46% in male and female subjects with androgenetic alopecia. Subjects will be required to apply ATI-50002 study medication to their scalp twice a day for a total of 26 weeks. Subjects will have the option to consent to remain on study for an additional 26 weeks after Visit 10 is completed. All subjects will be required to complete a safety follow up visit 4 weeks after their last application of study medication.

A total of 24 subjects (12 males and 12 females) ages 18-50 years of age with a clinical diagnosis of AGA will be enrolled in the study. Male subjects must have a Norwood Hamilton classification of Type III vertex, IV or V and woman must have a Sinclair Grade of 2, 3 or 4.

Subjects will be required to have a small 1.9 cm diameter circle clipped to ~ 1 mm in length on their balding scalp. Subjects must also agree to have a dot tattoo applied in the center of the clipped area during Visit 2.

Subjects will be required to complete the following treatment visits:

Visit 1: Screening (Day -14-0)

Visit 2: Day 1

Visit 3: Day 21

Visit 4: Day 28

Visit 5: Day 56

Visit 6: Day 84

Visit 7: Day 112

Visit 8: Day 140

Visit 9: Day 168

Visit 10: Day 182

Subjects that consent to remain on study for an additional 6 months of treatment will have the following study visits:

Visit 11: Week 30

Visit 12: Week 35

Visit 13: Week 39

Visit 14: Week 44

Visit 15: Week 48

Visit 16: Week 52

All subjects will be required to have a Follow up Safety Visit 4 weeks post last application of study medication.

All protocol defined treatment assessments are outlined in [Table 2](#) .

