## **7.2. Number of Subjects**

A total of 24 evaluable subjects will be enrolled to the study (12 male and 12 female) at approximately 3 investigational centers.

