## **13. STATISTICS**

### **13.1. Statistical Methods**

Summary descriptive statistics (N, mean, median, SD) by visit will be provided for all safety and efficacy parameters. The Intent to Treat population will be used for all efficacy assessments and the Safety population will be used for all safety assessments. No data imputation will be used. Primary and secondary efficacy parameters are described in the sections below.

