### **13.2. Primary Efficacy Endpoint**

Mean change from baseline in non-vellus TAHC will be quantified using a microphotographic technique and calculated along with the median, standard deviation, standard error, and 95% confidence limits around each mean change to allow tests of the null hypothesis that the population mean changes are zero.

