Visit	Statistic	Value	Change	Value	Change	Value	Change
D 1' a							
Baseline ^a	n	XX		XX		XX	
	Mean (SD)	xx.x(xx.xx)		xx.x (xx.xx)		xx.x(xx.xx)	
	SE	X.XX		X.XX		X.XX	
	Median	XXX.X		XXX.X		XXX.X	
	(Min, Max)	(xxx, xxx)		(xxx,xxx)		(xxx,xxx)	
V5 – Week 8	n	XX	XX	XX	XX	XX	xx
	Mean (SD)	xx.x (xx.xx)					
	SÈ	x.xx	X.XX	X.XX	x.xx	x.xx	x.xx
	Median	XXX.X	XXX.X	XXX.X	xxx.x	XXX.X	XXX.X
	(Min, Max)	(xxx,xxx)	(xxx, xxx)	(xxx,xxx)	(xxx,xxx)	(xxx,xxx)	(xxx,xxx)
	[95% CI] ^b	()	[xx.x, xx.x]	(,)	[xx.x, xx.x]	(;)	[xx.x, xx.x]
V7– Week 16	n	XX	XX	XX	XX	XX	XX
	Mean (SD)	xx.x (xx.xx)	xx.x (xx.xx)	xx.x (xx.xx)	xx.x(xx.xx)	xx.x (xx.xx)	xx.x (xx.xx)
	SE	x.xx	X.XX	X.XX	x.xx	X.XX	x.xx
	Median	XXX.X	XXX.X	XXX.X	xxx.x	XXX.X	xxx.x
	(Min, Max)	(xxx,xxx)	(xxx,xxx)	(xxx,xxx)	(xxx, xxx)	(xxx,xxx)	(xxx, xxx)
	[95% CI] ^b	())	[xx.x, xx.x]	()	[xx.x, xx.x]	()	[xx.x, xx.x]

 ^a Baseline is selected as the last measurement prior to the first application of study medication.
 ^b Confidence interval for the change from baseline.

Protocol: ATI-50002-AGA-201

Table 14.2.1.1 Non-Vellus Target Area Hair Count: Mean and Mean Change from Baseline (hairs/cm²) ITT Population

		Fen	nale	Ma	ale	To	tal
Visit	Statistic	Value	Change	Value	Change	Value	Change
V10-Week 26	n Mean (SD) SE Median (Min, Max) [95% CI] ^b	xx xx.x (xx.xx) x.xx xxx.x (xxx ,xxx)	XX XX.X (XX.XX) X.XX XXX.X (XXX ,XXX)	xx xx.x (xx.xx) x.xx xxx.x (xxx ,xxx)	XX XX.X (XX.XX) X.XX XXX.X (XXX, XXX)	xx xx.x (xx.xx) x.xx xxx.x (xxx ,xxx)	XX XX.X (XX.XX) X.XX XXX.X (XXX, XXX)
V16-Week 52	n Mean (SD) SE Median (Min, Max) [95% CI] ^b	xx xx.x (xx.xx) x.xx xxx.x (xxx ,xxx)	[xx.x, xx.x] xx xx.x (xx.xx) x.xx xxx.x (xxx, xxxx) [xx.x, xx.x]	xx xx.x (xx.xx) x.xx xxx.x (xxx ,xxx)	[xx.x, xx.x] xx xx.x (xx.xx) x.xx xxx.x (xxx, xxxx) [xx.x, xxxx)	xx xx.x (xx.xx) x.xx xxx.x (xxx ,xxx)	[xx.x, xx.x] xx xx.x (xx.xx) x.xx xxx.x (xxx, xxxx) [xx.x, xx.x]

^a Baseline is selected as the last measurement prior to the first application of study medication.

Repeat Format for

Table 14.2.1.2 Vellus Target Area Hair Count: Mean and Mean Change from Baseline (hairs/cm²) ITT Population

Table 14.2.1.3 Total (Non-Vellus + Vellus) Target Area Hair Count: Mean and Mean Change from Baseline (hairs/cm²) ITT Population

Table 14.2.1.4 Non-Vellus Target Area Hair Width: Mean and Mean Change from Baseline (cm) ITT Population

Table 14.2.1.5 Vellus Target Area Hair Width: Mean and Mean Change from Baseline (cm) ITT Population

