^b The number of patients with a non-missing score baseline and at the visit indicated. Used as denominator for percentages.

^c Includes early terminations or follow-ups collected during the first 26 Weeks or during the additional six months for patients opting to continue treatment in the optional six month extension. Additional rows provided to further sub-divide based on the period (1st 26 Weeks vs 6 Month Extension) and termination status (early termination vs follow-up).

Protocol: ATI-50002-AGA-201

Table 14.2.6 Correlation of Selected Effiacy Measures ITT Population

Visit	Parameter → ↓	Change in Nonvellus Target Area Hair Count		Change in Nonvellus Target Average Area Hair Width	Investigator Global Assessment	Subject Self Assessment
V5 – Week 8	Change in Nonvellus Target Area Hair Count	Corr=1	Corr=0.xx P-Value=0.xxxx	Corr=0.xx P-Value=0.xxxx	Corr=0.xx P-Value=0.xxxx	Corr=0.xx P-Value=0.xxxx
	Change in Nonvellus Target Area Hair Width		Corr=1	Corr=0.xx P-Value=0.xxxx	Corr=0.xx P-Value=0.xxxx	Corr=0.xx P-Value=0.xxxx
	Change in Nonvellus Target Area Average Hair Width			Corr=1	Corr=0.xx P-Value=0.xxxx	Corr=0.xx P-Value=0.xxxx
	Investigator Global Assessment				Corr=1	Corr=0.xx P-Value=0.xxxx
V7–Week 16 V10–Week 26 V16 – Week 52						

Note: Correlations are Pearson Correlations

Table 14.2.7 Correlation of Nonvellus Hair Count and Width Measures with Time Since Diagnosis of Androgenetic Alopecia ITT Population

Visit	Parameter → ↓	Time Since Diagnosis of Androgenetic Alopecia	
V5 – Week 8	Change in Nonvellus Target Area Hair Count	Corr=0.xx P-Value=0.xxxx	
	Change in Nonvellus Target Area Hair Width	Corr=0.xx P-Value=0.xxxx	
	Change in Nonvellus Target Area Average Hair Width	Corr=0.xx P-Value=0.xxxx	
V7–Week 16 V10–Week 26 V16 – Week 52			

Note: Correlations are Pearson Correlations

Aclaris Therapeutics Inc.

Protocol: ATI-50002-AGA-201

23 Apr 2019 Statistical Analysis Plan

Table 14.3.1 Summary of Treatment-Emergent Adverse Events Safety Population

	Female (N=xx) n (%)	Male (N=xx) n (%)	Total (N=xx) n (%)
Any Adverse Event	xx (xx.x)	xx (xx.x)	xx (xx.x)
Any Treatment-Related Adverse Event	xx (xx.x)	xx (xx.x)	xx (xx.x)
Any Serious Adverse Event	xx (xx.x)	xx (xx.x)	xx (xx.x)
Any Adverse Event Resulting in Study Discontinuation	xx (xx.x)	xx (xx.x)	xx (xx.x)

n = number of patients with treatment emergent adverse event(s).

NOTE: Patients with multiple occurrences of a preferred term are counted only once for that term.

Table 14.3.1.1

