>1.5xULN Alk Phos	x(x.x)	x(x.x)	x(x.x)
Elevation of AT ^b and Bilirubin			
>3xULN AT and >1.5xULN Bilirubin	x(x.x)	x(x.x)	x(x.x)
>3xULN AT and >2xULN Bilirubin	x(x.x)	x(x.x)	x(x.x)
>3xULN AT and >=2xULN Bilirubin and Alkaline Phosphatase <2xULN or missing	x(x.x)	x(x.x)	x(x.x)

^a Patients with both ALT and AST abnormalities for the same lab draw (same date and time) are counted as one event.

PROGRAMMING NOTE: It is intentional that the last criterion has '=' added to the bilirubin threshold – to match exactly FDA Guidance doc

[figure not shown]
^b AT = aminotransferase. Either AST or ALT (or both) elevated.

23 Apr 2019 Statistical Analysis Plan

Table 14.3.6 Number and Percent of Patients Meeting Laboratory Criteria for Potential Renal Impairment Safety Population

Criteria	Female (N=xx) n (%)	Male (N=xx) n (%)	Total (N=xx) n (%)	
Change from Baseline ≥ 0.5 mg/dL	x (x.x)	x (x.x)	x (x.x)	
>1.5xULN Creatinine	x(x.x)	x(x.x)	x(x.x)	
EITHER Change from Baseline >=0.5 mg/dL or >1.5xULN Creatinine	x(x.x)	x(x.x)	x(x.x)	
BOTH Change from Baseline >= 0.5 mg/dL and >1.5xULN Creatinine	x(x.x)	x(x.x)	x(x.x)	

Figure 14.1
Association of Selected Efficacy Measures with Fit Linear Regression Line
ITT Population: Visit = V5 Week 8

Reperat for:

Figure 14.2	Association of Selected Efficacy Measures with Fit Linear Regression Line, ITT Population: Visit=V7 Week 16
Figure 14.3	Association of Selected Efficacy Measures with Fit Linear Regression Line, ITT Population: Visit=V10 Week 26
Figure 14.4	Association of Selected Efficacy Measures with Fit Linear Regression Line, ITT Population: Visit=V16 Week 52

For the following plot change in averge hair wdth (vertical) vs Investigaor Global Assessment [4 figures – All timepoints on page]. Indicate timepoint at top of each of the visits. Separate color for males and females and linear regression line as per figure 14.1.Add Foonote: Note Lines represent fit linear regression line.

Figure 14.5 Association of Change in Nonvellus Target Area Average Hair Width with Investigator Global Assessment, ITT Population

For the following plot change in averge hair wdth (vertical) vs Subject Self Assessment [4 figures – All timepoints on page] Indicate timepoint at top of each of the visits. Separate color for males and females and linear regression line as per figure 14.1.Add Foonote: Note Lines represent fit linear regression line.

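### SAP Tables 14.2.6 and 14.2.7 pool men and women in every correlation, so a p-value can reflect a difference between the sexes rather than an association within either

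*SAP*

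**What the plan says.** Protocol 7.1 plans "A total of 24 subjects (12 males and 12 females) ages 18-50 years of age with a clinical diagnosis of AGA". The Synopsis is softer: "Approximately 12 male subjects and 12 female subjects will be enrolled to the study".

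SAP Tables 14.2.1.x to 14.2.3.x (hair counts, hair widths, investigator and subject scores) have Female, Male and Total columns. Tables 14.2.6 and 14.2.7 do not. Table 14.2.6 correlates five measures with one another: change in non-vellus count, width and average width, and the two global scores. Table 14.2.7 correlates the three hair measures with time since diagnosis. Both print a coefficient and a p-value at Weeks 8, 16, 26 and 52, and both carry the note "Note: Correlations are Pearson Correlations". Neither mock-up shows a sex split or a sex adjustment.

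For the primary endpoint, Protocol 13.2 asks for "95% confidence limits around each mean change to allow tests of the null hypothesis that the population mean changes are zero". In Table 14.2.1.1 the interval appears under Female, Male and Total, and its footnote reads only "Confidence interval for the change from baseline".

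**The concern.** A correlation pooled over two groups mixes the association within each group with the difference between the group means. If men and women differ on both variables, the pooled coefficient moves away from zero even when nothing links the variables among men or among women.

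The documents give reasons to expect such differences on some of these variables. Protocol 11.3 and Appendix 4 (section II) take vertex photographs in men only and frontal photographs in both sexes, so the investigator and subject scores are not based on the same views. Protocol 5.1 describes different patterns of loss. The SAP itself summarises time since diagnosis by sex in Table 14.1.3.

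What is at stake is interpretation. These tables would be used to argue that a gain in hair count or width is visible to the investigator or the subject, or that response depends on disease duration. A p-value produced by the sex contrast supports neither claim.

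**Working it through.** **Inputs.** From the documents: 12 men and 12 women (Protocol 7.1), Pearson correlation with p-value (SAP Tables 14.2.6 and 14.2.7), and no imputation (Protocol 13.1). The documents give no SDs, no sex differences and no expected correlations, so there is no figure of the plan's own to reproduce. Assumptions: normal data, within-sex SD 1 on each variable, within-sex correlation 0, and sex differences D1 and D2 in SD units, shown over a range. The 0.05 two-sided level is also assumed for these tables.

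**Number of p-values.** Five measures give 10 pairs, and 10 × 4 visits = 40. Table 14.2.7 adds 3 × 4 = 12. The total is 52.

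**Induced correlation.** With an equal split, sex contributes variance D²/4 to each variable and covariance D1·D2/4 to the pair:

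ρ = (D1·D2/4) / √[(1 + D1²/4)(1 + D2²/4)]

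When D1 = D2 = 1 this is 0.25/1.25 = 0.20. When D1 = D2 = 1.5 it is 0.5625/1.5625 = 0.36. If either D is zero, ρ = 0.

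**Rejection threshold.** With n = 24 the pooled test has 22 df and t = 2.0739. It rejects when |r| exceeds 2.0739/√(2.0739² + 22) = 0.404.

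**Simulated false-positive rate** (nominal 5%, no association within either sex):

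| D1, D2 | Induced ρ | Pooled Pearson | Sex-adjusted (21 df) |
|---|---|---|---|
| 0, 0 | 0 | 5% | 5% |
| 1, 0 | 0 | 5% | 5% |
| 0.5, 0.5 | 0.06 | 6% | 5% |
| 1, 0.5 | 0.11 | 8% | 5% |
| 1, 1 | 0.20 | 16% | 5% |
| 1.5, 1 | 0.27 | 25% | 5% |
| 1.5, 1.5 | 0.36 | 45% | 5% |

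**Secondary check: the Total interval.** Suppose it is mean ± t(23)·s/√24. With 12/12 held fixed, E[s²] = σ²(1 + 6D²/23). The width relative to an interval built on the within-sex SD with 22 df is then about √(1 + 6D²/23) × 2.0687/2.0739. At D = 0.5, 1.0 and 1.5 this gives 1.03, 1.12 and 1.26. Simulated coverage is 95.6%, 97.1% and 98.5%. If sex were random rather than a quota, coverage would be 95.0%.

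**Would an equal-weight, pooled-SD interval be better?** At an assumed 6 women and 10 men:
- With equal SDs and no sex difference, its mean half-width is 0.544 SD against 0.524 for the plain interval, about 4% wider (0.544/0.524 = 1.04).
- At a sex difference of 0.5 SD it is still no narrower (0.544 against 0.540).
- If the smaller group's SD is 1.5 or 2 times the other's, its coverage falls to about 92% or 90%.

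**The case against.** **The correlations are exploratory.** They are not protocol endpoints and no decision is tied to them. This stands, and it limits the weight of the point. It does not make an uninterpretable p-value worth printing.

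**The figures separate the sexes.** The notes for Figures 14.5 to 14.9 call for "Separate color for males and females and linear regression line as per figure 14.1". A careful reader of the plots could see a sex contrast. The colours leave the tabulated coefficients and p-values unchanged, however, and the note does not settle whether there is one regression line or one per sex.

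**Both variables must differ.** Inflation is negligible if only one does and small at 0.5 SD on each. The 45% figure needs 1.5 SD on both, and the documents give no sex difference for any of these variables. This also stands, and it is why the result is given as a range.

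**A pooled correlation is a legitimate quantity.** It describes association in the mixed group. That is true, but it is not the association within men or women that these tables would be read to show.

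**A stronger reading that the documents do not support.** A reader might infer that the Total interval for the primary endpoint is wrong and must be replaced by a sex-stratified one. Several things stand against this:
- No formula is visible. The SAP text available for review begins at the list of tables, so a plain one-sample interval is likely from the SD and SE layout but not certain.
- The 12/12 split is only approximate in the Synopsis. Because "No data imputation will be used" and the extension is optional, the observed split can change by visit.
- Female and Male intervals stand beside Total, and no document makes Total the primary column.
- Hair count is measured the same way in both sexes, by blinded technicians (Protocol 11.1, Appendix 5).
- Any error is conservative, and about 3% in width at 0.5 SD.

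**Conclusion.** The point holds for Tables 14.2.6 and 14.2.7. As laid out, their p-values cannot distinguish an association within the sexes from a difference between them. The false-positive rate is about 6%, 16% and 45% at sex differences of 0.5, 1.0 and 1.5 SD on both variables, and 5% if only one differs. Sex adjustment restores 5% throughout. These figures rest on 12 + 12 observed subjects, normal data and assumed sex differences. The layout is visible in the mock-ups, but any SAP methods text before the table list could not be checked.

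The Total interval in Table 14.2.1.1 merits only a note. If it is a plain one-sample interval, it is mildly conservative when mean change differs by sex, and it creates no false positives.

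**What to change.** In Tables 14.2.6 and 14.2.7, add Female and Male correlations and make the pooled value a partial correlation adjusted for sex. No new data are needed. The adjusted test uses 21 df instead of 22, so its threshold rises from |r| = 0.404 to 2.0796/√(2.0796² + 21) = 0.413, and the tables grow slightly. The by-sex values will be imprecise: with 12 subjects (10 df, t = 2.2281), |r| must exceed 2.2281/√(2.2281² + 10) = 0.576 to reach 0.05. They are best labelled descriptive.

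For Table 14.2.1.1, state the formula of the Total interval and add that Total is to be read with the Female and Male columns. Replacing it with an equal-weight, pooled-SD interval is optional. That changes the estimand and can lose width or coverage once the sex split is unbalanced.

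Rank correlation for pairs involving the seven-point scores is also optional and a separate matter from sex.

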### **13.3. Secondary Efficacy Endpoints**

Mean change from baseline in cumulative TAHW will be quantified using a microphotographic technique and calculated along with the median, standard deviation, standard error, and 95% confidence limits around each mean change to allow tests of the null hypothesis that the population mean changes are zero.

The seven-point rating scale to measure the investigator and subject assessment of the development of new hair growth/scalp coverage will be analyzed with summary statistics (N, mean, median, SD) for each visit where the assessment is made. Similar summary statistics will be used to analyze change from baseline in AGA stage separately for males (Horwood Hamilton Scale) and for females (Sinclair Scale) at each applicable visit.

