Table 14.2.1.6 Total (Non-Vellus + Vellus) Target Area Hair Width: Mean and Mean Change from Baseline (cm) ITT Population

 Table 14.2.1.7
 Average Non-Vellus Hair Width: Mean and Mean Change from Baseline (cm) ITT Population

Footnote for 14.2.1.7: Note: Average non-vellus hair width is calculated for each patient as the non-vellus target area count divided by the non-vellus target area hair width

^b Confidence interval for the change from baseline.

23 Apr 2019 Statistical Analysis Plan

Table 14.2.2.1 Investigator Global Assessment ITT Population

		ITT Population		
Visit	Statistic	Female	Male	Total
V5 – Week 8	n	XX	XX	VV
v 5 – vv eek o	Mean (SD)			XX
	` ,	xx.x (xx.xx)	xx.x (xx.xx)	xx.x (xx.xx)
	Median	xxx.x	XXX.X	XXX.X
	(Min, Max)	(xxx,xxx)	(xxx,xxx)	(xxx, xxx)
V7– Week 16	n	XX	xx	XX
	Mean (SD)	xx.x (xx.xx)	xx.x (xx.xx)	xx.x (xx.xx)
	Median	xxx.x	XXX.X	XXX.X
	(Min, Max)	(xxx,xxx)	(xxx,xxx)	(xxx,xxx)
V10-Week 26	n	XX	XX	XX
	Mean (SD)	xx.x (xx.xx)	xx.x (xx.xx)	xx.x (xx.xx)
	Median	XXX.X	XXX.X	XXX.X
	(Min, Max)	(xxx, xxx)	(xxx, xxx)	(xxx, xxx)
V13-Week 39	n	XX	XX	XX
	Mean (SD)	xx.x (xx.xx)	xx.x (xx.xx)	xx.x (xx.xx)
	Median	XXX.X	XXX.X	XXX.X
	(Min, Max)	(xxx,xxx)	(xxx,xxx)	(xxx,xxx)
V16 – Week 52	n	XX	XX	XX
	Mean (SD)	xx.x (xx.xx)	xx.x(xx.xx)	xx.x(xx.xx)
	Median	XXX.X	XXX.X	XXX.X
	(Min, Max)	(xxx, xxx)	(xxx, xxx)	(xxx, xxx)
FU/Early Termination	n	XX	XX	XX
1 C. Larry 1 Crimmunon	Mean (SD)	xx.x (xx.xx)	xx.x (xx.xx)	xx.x (xx.xx)
	Median	XXX.X	XXX.X	XXX.X
	(Min, Max)			
	(IVIIII, IVIAX)	(xxx ,xxx)	(xxx ,xxx)	(xxx, xxx)

Repeat Format for

 Table 14.2.2.2
 Subject Self-Assessment ITT Population

Aclaris Therapeutics Inc.

Protocol: ATI-50002-AGA-201

23 Apr 2019 Statistical Analysis Plan

Table 14.2.3.1
Investigator Global Assessment: Patients with Slightly Increased Hair Growth or Better (Grade +1 to +3)
ITT Population

Visit	Statistic	Female	Male	Total
V5 – Week 8	N^a n (%)	xx xx (xx.x)	xx xx (xx.x)	xx xx (xx.x)
V7- Week 16	N^a n (%)	xx xx (xx.x)	xx xx (xx.x)	xx xx (xx.x)
V10-Week 26	N^a n (%)	xx xx (xx.x)	xx xx (xx.x)	xx xx (xx.x)
V13-Week 39	N^a n (%)	xx xx (xx.x)	xx xx (xx.x)	xx xx (xx.x)
V16 – Week 52	N^a n (%)	xx xx (xx.x)	xx xx (xx.x)	xx xx (xx.x)
FU/Early Termination	N^a n (%)	xx xx (xx.x)	xx xx (xx.x)	xx xx (xx.x)

Repeat Format for

Table 14.2.3.2 Subject Self-Assessment: Patients with Slightly Increased Hair Growth or Better (Grade +1 to +3) ITT Population

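### The footnote to SAP Table 14.2.1.7 inverts the formula for average non-vellus hair width; programmed as written, it reverses every patient's direction of change and distorts the group results

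*SAP*

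**What the plan says.** Protocol Section 13.3 makes TAHW a cumulative quantity: "Mean change from baseline in cumulative TAHW will be quantified using a microphotographic technique". Protocol Appendix 5, Section VII, explains how it arises: each hair inside a 1 cm² circle is measured individually.

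The SAP table shells fix the units:

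- Table 14.2.1.1 (count): "Non-Vellus Target Area Hair Count: Mean and Mean Change from Baseline (hairs/cm²) ITT Population"
- Table 14.2.1.4 (cumulative width): "Non-Vellus Target Area Hair Width: Mean and Mean Change from Baseline (cm) ITT Population"
- Table 14.2.1.7 (average width): "Average Non-Vellus Hair Width: Mean and Mean Change from Baseline (cm) ITT Population"

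The footnote to Table 14.2.1.7 then defines the average: "Average non-vellus hair width is calculated for each patient as the non-vellus target area count divided by the non-vellus target area hair width".

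A variable labelled "Change in Nonvellus Target Area Average Hair Width" appears in the Pearson correlation tables (14.2.6 and 14.2.7). It is plotted with regression lines in Figures 14.5, 14.6 and 14.9; Figure 14.5, for example, is titled "Association of Change in Nonvellus Target Area Average Hair Width with Investigator Global Assessment, ITT Population".

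**The concern.** A mean is a sum divided by a count. TAHW is the sum of the hair widths and the target area hair count (TAHC) is the number of hairs, so average width is TAHW/TAHC. The footnote has the division the other way up, and the result contradicts both the name and the unit of its own table.

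This is the variable that asks whether individual hairs thicken. Neither the count nor the cumulative width isolates that, since cumulative width also rises when hairs are added. If the footnote is followed, thickening is tabulated as a loss, and the associations with the investigator and subject ratings and with time since diagnosis are likely to point the wrong way. The error need not be obvious on the page: the inverted values fall in the hundreds and print cleanly in the shell's number format, whereas correct values in cm would not.

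**Working it through.** The documents state no figure for average hair width, so there is nothing to reproduce. All hair widths, counts and SDs below are assumptions chosen to show direction and size.

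**1. Units.** Let C be the count on the 1 cm² target area and W the cumulative width in cm.

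- W/C is in cm per hair, which matches the table title.
- C/W is in hairs per cm, which does not.

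For 150 hairs of 60 µm (0.006 cm), W = 150 × 0.006 = 0.90 cm. Then W/C = 0.006 cm and C/W = 166.7 per cm. Appendix 5 classes hairs above 30 µm as terminal. If non-vellus means the same (the documents do not say so), W/C must exceed 0.003 cm and C/W must be below 1/0.003 = 333 per cm.

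**2. One patient.** With average width b at baseline and f at follow-up, the footnote's change is

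1/f − 1/b = −(f − b)/(b × f).

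Widths are positive, so the sign is always opposite to f − b unless the change is zero. With the count fixed and every hair 10% thicker:

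| Hairs | Baseline width | True change | Change as written (per cm) |
|---|---|---|---|
| 100 | 50 µm | +5 µm | 100/0.55 − 100/0.50 = −18.2 |
| 150 | 60 µm | +6 µm | 150/0.99 − 150/0.90 = −15.2 |
| 200 | 70 µm | +7 µm | 200/1.54 − 200/1.40 = −13.0 |

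Each true change is +10%; each change as written is 1/1.1 − 1 = −9.1%.

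**3. Distortion.** The divisor b × f differs between patients. Take the same +6 µm gain, with widths in µm:

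- from 40 µm: 10,000/46 − 10,000/40 = −32.6 per cm
- from 80 µm: 10,000/86 − 10,000/80 = −8.7 per cm

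The ratio is (80 × 86)/(40 × 46) = 3.7. Thin-haired patients dominate the mean, so multiplying the output by −1 does not recover the correct result.

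**4. Groups: reversal is usual, not certain.** Two counterexamples keep the same sign:

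- *Mean.* Two patients go from 40 to 36 µm and from 80 to 90 µm. Mean width change is (−4 + 10)/2 = +3 µm. Mean reciprocal change is (27.8 − 13.9)/2 = +6.9 per cm.
- *Correlation.* Baseline widths 40, 45, 80, 85, 60; follow-up 44, 49, 86, 91, 60; ratings 2, 1, 1, 0, 1. Pearson r is −0.29 on width change and −0.59 on reciprocal change.

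Two sets of simulations show how often the sign flips. The planned sample is 24 (Protocol Section 7.2).

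| Assumed inputs | Mean change reversed | Pearson r with a rating reversed |
|---|---|---|
| n = 24; baseline mean 60 µm, SD 8 or 12; mean change 0, 3 or 6 µm, SD 5; true correlation 0 to 0.6 | 83–100% | 82–100% |
| n = 12 or 24; baseline mean 55 µm, SD 5 to 15; mean change −6 to +6 µm, SD 2 or 6; true correlation 0 or 0.5 | 80–100% | 63–100% |

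The lowest rates for the mean occur when the true mean change is zero. The lowest rates for r occur when there is no true correlation, the change is large and nearly uniform, and baseline widths are widely spread; in those settings r has no meaningful sign to reverse. Where an association exists the flip is nearly certain but the size is off: with baseline SD 12 µm, mean change 6 µm and true correlation 0.6, median r is +0.58 on width and −0.49 on the reciprocal.

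**The case against.** The strongest reply is that this is a slip in a table-shell footnote. The title beside it has the right name and unit, the cm label suggests that width over count was intended, and the documents do not show the code. That stands as a limit: every numerical consequence above is conditional on the footnote being programmed as written. It does not rescue the text. If the code is correct, the printed footnote still misdescribes the table.

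Other points that stand in part:

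- The SAP text available for this review begins at the lists of tables and figures, so a correct definition elsewhere in the SAP cannot be excluded. It would leave the footnote in conflict with it.
- The formula is attached to Table 14.2.1.7 only. That the correlation tables and figures share the derivation is a strong inference from their labels, not something the SAP states.
- For Pearson correlations, distortion is general but not universal: the size of r is unchanged in degenerate cases, such as two patients or a constant product of baseline and follow-up width.
- The simulated rates depend on assumed inputs and cover only correlation with a rating, not with change in count, change in cumulative width or time since diagnosis.
- Count and cumulative width are tabulated separately, so an alert reader could detect the inversion from values in the hundreds under a cm heading.

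None of this alters the error or its remedy.

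**Conclusion.** The footnote is wrong as written. That follows from the SAP's own units and needs no assumption about the data. If it is programmed literally, the reversal of each patient's non-zero change is exact. Group means are always on the wrong scale and usually have the wrong sign; Pearson correlations and regression lines are usually reversed and generally altered in size. The reversal rates rest on assumed widths and spreads.

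The reach is limited. The primary endpoint and the secondary endpoint of cumulative TAHW do not use the variable and are unaffected. What is at risk is the supportive reading on hair calibre and its associations. The correction should be made, but it does not threaten the main efficacy analysis.

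**What to change.** Reword the footnote so that average non-vellus hair width is the non-vellus target area hair width divided by the non-vellus target area hair count. Check the derivation in the code. Derive Tables 14.2.1.7, 14.2.6 and 14.2.7 and Figures 14.5, 14.6 and 14.9 from the corrected variable, and check whether Figures 14.1 to 14.4 also use it. Re-run any output already produced with the inverted formula; do not flip signs on it.

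A separate formatting point: Table 14.2.1.7 inherits a one-decimal shell, which would print 0.006 cm as 0.0. Report in micrometres (TAHW in cm × 10,000 / TAHC) or use at least four decimals in cm.

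The cost is one line of SAP text and, if the error was coded, one line of program plus the re-run. No further data are needed.
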